## 15. Analysis of Exploratory Endpoints

The analysis will be based on the ITT Population corresponding to each outcome. Missing data will not be imputed and endpoints will not be tested statistically. Endpoints will be presented descriptively by treatment arm.

- **Oxygen saturation on room air**

The associated endpoint is “trend of improvement of SpO2 on room air from Baseline (Day 1) to Day 33.” A side-by-side box plot of SpO2 level by treatment group will be provided.

- **Modified Borg Dyspnea Scale Score at Baseline (Day 1) and on Days 7, 14, 21, and 33**

The associated endpoints are “changes in modified Borg Dyspnea Scale from baseline (Day 1) to Days 7, 14, 21 and 33.” Descriptive statistics for crude value and absolute changes from baseline (e.g. Day 7 measurement minus baseline measurement) by treatment arm and overall will be provided for the ITT Population. Moreover, descriptive statistics for difference in change from baseline between the treatment arms will be provided for each time point. Descriptive statistics, least squares means, standard errors, and 95% CIs for mean differences will be presented. Least squares estimates presented at each visit will be based on ANCOVA models with baseline value and age category as covariates.

- **MQoL-SIS score at Baseline (Day 1) and on Days 7, 14, 21 and 33**

The associated endpoints are “changes in MQoL-SIS score from baseline (Day 1) to Days 7, 14, 21 and 33.” Descriptive statistics for crude value and absolute changes from baseline (e.g. Day 7 measurement minus baseline measurement) by treatment arm and overall will be provided for the ITT Population. Moreover, descriptive statistics for difference in change from baseline between the treatment arms will be provided for each time point. Descriptive statistics, least squares means, standard errors, and 95% CIs

for mean differences will be presented. Least squares estimates presented at each visit will be based on ANCOVA models with baseline value and age category as covariates.

## **16. Safety Analysis**

This analysis will be based on the Safety Analysis Population and will be presented by treatment arms as well as overall.

All AEs will be tabulated by severity from baseline up to Day 33 after first dose.

All AEs will be coded using the MedDRA dictionary Version 23.0 or higher. The severity of AEs will be graded 1 to 5 according to the National Cancer Institute Common Terminology Criteria for Adverse Events (NCI-CTCAE) Version 5.0. AEs with missing severity will be presented in the summary table as CTCAE Grade 3.

A treatment-emergent adverse event (TEAE) is defined as an AE which started on or after the first dosing date of the study drug or an existing condition becoming worse on or after the first dosing date of the study drug. Adverse events with unknown onset date and with end date after first dosing date will be counted as a TEAE, unless it can be definitely shown that the condition was already present before the first dosing.

A treatment-related AE is defined as an AE which has a suspected relationship to the study drug, i.e. which has been rated as possibly or probably related by the investigator. Adverse events with missing relationship to study drug will be assessed as treatment-related.

The following summaries will be provided:

- A table for overall summary and a listing of all AEs that occurred during the screening period by SOC and PT will be provided.
- The following summary tables will be generated for AEs occurring from randomization date to Day 33:
  - Overall summary
  - All TEAEs
  - TEAEs leading to discontinuation of treatment

- TEAEs with toxicity grade  $\geq 3$
- Drug-related TEAEs
- Serious TEAEs
- TEAEs that led to death

Unless otherwise specified, AEs will be summarized by treatment group, SOC and PT. All TEAEs will be summarized by maximum toxicity grade, SOC, and PT.

If a subject experiences multiple AEs in the same SOC, that subject will be counted only once for that SOC. If a subject experiences multiple AEs under the same PT, then the subject will be counted only once for that PT. If a subject experiences the same AE more than once with different toxicity grades, the event with the highest grade will be tabulated in maximum toxicity grade tables.

Absolute change in vital signs and clinical laboratory parameters from baseline to each study visit up to Day 33 will be summarized descriptively with mean, standard deviation, median, range and 95% confidence intervals. The clinically significant status of vital signs will also be tabulated.

No missing data will be imputed, and no formal hypothesis testing will be performed for safety endpoints.

Subject level listings of AEs, vital signs, clinical laboratory parameters and inflammation assessment will be provided.

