4.3 Withdrawal and Replacement of Subjects

4.3.1 Premature Subject Withdrawal

Subjects have the right to withdraw from the study at any time for any reason, without the need to justify their decision. The Investigator also has the right to withdraw subjects in case of AEs, poor compliance, or other reasons. Since an excessive rate of withdrawals can render the study non-interpretable, any unnecessary withdrawal of subjects should be avoided.

In addition to the ongoing safety monitoring and periodic Independent Data Monitoring Committee (IDMC) data review, the following rule will be implemented to apply temporary suspension of study drug administration, pending a safety investigation, for an unacceptable increased venous TEE or acute renal failure risk in the *Octagam 10%* group compared to the placebo group:

- For both venous TEEs or acute renal failures, the event risk will be calculated separately as (number of events reported)/(number of daily infusions) in both treatment groups, and the 90% confidence interval (CI) for the resulting risk ratio (R_{Octagam}/R_{Placebo}) will be determined by means of the / relrisk option of the SAS procedure FREQ. In case no events are observed in the placebo group, 1 will be added to each cell in the 2X2 table to enable this risk ratio evaluation. The stopping rule will be triggered if the lower confidence limit is greater than 1.0.
- This stopping rule will be applied whenever an unblinded evaluation is done, and a total of 40 daily infusions or more have been administered.
- For the first 40 daily infusions (ie, first 10 subjects that complete infusion cycle per protocol) a fixed rule will be applied by the IDMC to temporarily suspend study drug administration in case the number of related serious TEEs or acute renal failures as assessed by IDMC in the *Octagam 10%* group is triple the number in the placebo group. If no TEE or acute renal failure is observed in the

placebo group during this initial study phase, temporary suspension of study drug administration and safety investigation will be initiated if three related serious TEEs as assessed by IDMC or acute renal failures have been reported in the *Octagam 10%* group.

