Events that will prevent the scheduled administration of study drug will include but not limited to:

- Uncontrolled blood pressure elevation (ie, systolic is \geq 160 mmHg or diastolic is \geq 90 mmHg)
- Chest pain with or without electrocardiogram changes
- Thrombotic events
- New onset seizures

- Acute Kidney Injury (AKI) as defined by KDIGO Clinical Practice Guideline for AKI as any of the following:
 - Increase in serum creatinine by ≥ 0.3 mg/dl (≥ 26.5 $\mu\text{mol/l}$) within 48 hours
 - or Increase in serum creatinine to ≥ 1.5 times baseline, which is known or presumed to have occurred within the prior 7 days
 - or Urine volume < 0.5 ml/kg/h for 6 hours
- Stroke
- Myocardial infarction.

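### The final safety tables report adverse events only by system organ class and preferred term, so subjects per arm with any thromboembolic event, a risk the protocol singles out, are not counted

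*SAP*

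**What the plan says.** **During conduct.** Protocol 4.3.1 sets a suspension rule for two named risks: "For both venous TEEs or acute renal failures, the event risk will be calculated separately". The measure is "number of events reported)/(number of daily infusions) in both treatment groups", compared between arms as a risk ratio with a 90% confidence interval: "The stopping rule will be triggered if the lower confidence limit is greater than 1.0". The rule belongs to monitoring: "This stopping rule will be applied whenever an unblinded evaluation is done", from 40 daily infusions on. Before that a fixed rule applies, "For the first 40 daily infusions (ie, first 10 subjects that complete infusion cycle per protocol", which refers to related serious thromboembolic events (without the word venous) and to acute renal failures.

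**At the final analysis.** SAP 16 lists an overall summary and tables of all treatment-emergent events, then those that led to discontinuation, were grade 3 or higher, drug-related, serious or fatal. The display level is "Unless otherwise specified, AEs will be summarized by treatment group, SOC and PT". The counting rule is "If a subject experiences multiple AEs in the same SOC, that subject will be counted only once for that SOC", with a parallel rule for each preferred term. SAP 18.3 adds laboratory CTCAE shifts and the incidence of high and low laboratory values. Protocol 9.2.4 plans the same kinds of tables. Subject-level adverse event listings are planned in SAP 16.

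Neither document defines an event of special interest, a term list or a grouped subject count for thromboembolic events or acute renal failure.

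**The concern.** The protocol treats these two risks as the ones that matter most for this product. They carry the suspension rule, they drive several exclusion criteria, and Protocol 5.4 asks for particular care in subjects at risk of either. A reader of the study report will therefore want to know how many subjects in each arm had at least one thromboembolic event, and the difference between arms with its uncertainty.

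The planned tables do not answer that. Protocol 4.1.2 (exclusion criterion 3) gives as examples of thromboembolic events deep vein thrombosis, pulmonary embolism, myocardial infarction, ischemic stroke and transient ischemic attack. These are separate diagnoses and can be expected to occupy separate rows. A subject with two of them is counted in two rows, so the rows cannot be added. If the grouping is first made after unblinding, the choice of terms is open to the objection that it was made with the result in view.

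**Working it through.** **1. The plan's own figures.** The early window reproduces: 10 subjects × 4 daily infusions = 40. The arm size reproduces: 88 / (1 − 0.15) = 103.5, rounded up to 104; 2 × 104 = 208. The point does not depend on an error in either.

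**2. The two stages side by side.**

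| | Suspension rule (Protocol 4.3.1) | Final analysis (SAP 16, 18.3; Protocol 9.2.4) |
|---|---|---|
| Thromboembolic events | Venous only in the risk-ratio rule; related serious events in the early rule | Not named |
| Acute renal failure | Named, calculated separately | Not named; laboratory shifts partly relevant |
| Unit | Events per daily infusion | Subjects, once per class and once per term |
| Comparison | Risk ratio, 90% CI | Counts by arm in each row; no grouped difference or interval |

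The number of subjects with any event in the group appears in neither column.

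**3. What the preferred-term rows can tell.** Let an arm of size *n* have row counts x₁, …, x_k for the thromboembolic terms. The number of subjects N with at least one event is bounded only by

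max(x₁, …, x_k) ≤ N ≤ min(n, x₁ + … + x_k).

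The lower limit is reached when the same subjects recur across rows, the upper when no subject has two diagnoses. System organ class rows also include other terms, so at best they narrow this range.

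**4. Illustration.** The counts are assumed and come from neither document; n = 104 per arm is the planned size.

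| Preferred term | IVIG | Placebo |
|---|---|---|
| Pulmonary embolism | 2 | 1 |
| Deep vein thrombosis | 2 | 0 |
| Myocardial infarction | 1 | 0 |
| Ischemic stroke | 2 | 1 |
| Transient ischemic attack | 1 | 0 |

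- IVIG: largest row 2, sum 8, so N lies between 2 (2/104 = 1.9%) and 8 (8/104 = 7.7%).
- Placebo: largest row 1, sum 2, so N lies between 1 (1/104 = 1.0%) and 2 (2/104 = 1.9%).
- Risk difference: from (2 − 2)/104 = 0 to (8 − 1)/104 = 6.7 percentage points.

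The lower limit for IVIG needs the same two subjects in almost every row, so it is an arithmetical limit and not an expectation. With little overlap the truth lies near the upper end.

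**5. Why the terms should be fixed in advance.** In the same table, taking only the first two rows as venous gives 2 to 4 subjects on IVIG against exactly 1 on placebo. All five rows give 2 to 8 against 1 to 2. The size of the result depends on the term set, which neither document fixes.

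**6. Renal failure.** Nothing in the documents shows that acute renal failure would be spread over many terms, and SAP 18.3 covers laboratory changes. The gap is narrower, but a count of affected subjects is still not planned.

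**The case against.** The strongest reply is that the plan is conventional and consistent. Tabulation by class and term follows Protocol 9.2.4, the safety objective is descriptive, and SAP 16 excludes formal safety testing. Incidence per preferred term is planned for all, serious, fatal, grade 3 or higher and drug-related events. Listings allow a grouped count by hand. SAP 8 plans a further monitoring committee meeting on complete data; if it is unblinded, Protocol 4.3.1 would give the committee a comparison between arms. The committee's charter is not among the documents. All of this stands, and it makes the point an improvement and not the correction of an error. It does not supply the missing count: the listings leave the term set open, and the committee's comparison is in events per infusion, venous only in the risk-ratio rule, and not a final-analysis output.

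Three stronger readings are tempting and are not supported.

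- A reader might infer that the SAP drops a grouping the protocol had set up. The risk-ratio rule never pooled venous with arterial events and never counted subjects.
- A reader might infer that the SAP should have applied the kidney injury definition in Protocol 5.4 ("Acute Kidney Injury (AKI) as defined by KDIGO Clinical Practice Guideline for AKI as any of the following"). There it is a reason to withhold a dose, not an endpoint. Scheduled sampling could apply it only in part: creatinine is drawn on Days 1 to 4, the next scheduled panel is Day 7, so a 48-hour change cannot be followed across that gap, and urine volume is not in the flow chart.
- A reader might want to show the loss by comparing p-values for grouped and split counts. Such counts would be invented, and if the rows summed exactly to the group there would be no overlap, the one case in which adding rows recovers the answer.

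**Conclusion.** The point holds as a gap in reporting. The planned summary tables do not give, and do not allow a reader to derive, the number of subjects per arm with any thromboembolic event. For acute renal failure the gap is smaller.

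Its size cannot be stated from the documents, which give no expected event rates. The illustration shows only that a few small rows can leave a grouped risk difference open over several percentage points. It rests on assumed counts and on the planned 104 per arm; the safety population may be smaller. The conclusion itself rests on two things: a subject may have more than one thromboembolic diagnosis, and neither document specifies a grouped output. No endpoint, test or sample size is affected.

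**What to change.** In SAP 16, add grouped events with term lists settled and documented at the blinded data review (SAP 7):

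1. any thromboembolic event, with venous and arterial events also shown separately;
2. acute renal failure, based on adverse event terms.

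For each, report by arm the number and percentage of safety-population subjects with at least one event, with the risk difference and 95% CI, descriptively and without a test.

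A renal count based on creatinine is optional. If included, label it as partial, because the sampling days and the lack of scheduled urine volume do not allow the full KDIGO definition.

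The two scopes in Protocol 4.3.1, venous events in one rule and related serious events in the other, should be reconciled or their difference explained when the term lists are written.

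The cost is a term list and a little more programming. No new data are needed.

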## **17. Additional Efficacy Analysis**

The proportions of subjects stabilized or improved will be provided at Day 21 and Day 33 for both treatment arms. No hypothesis testing will be made for this analysis, but the difference of proportions will be presented, together with its standard error and the associated 95% confidence interval.

The proportions and frequencies of subjects' clinical status will be summarized over time. Frequencies and proportions of oxygen ventilator status will be also summarized over time. No hypothesis testing will be made for this analysis, but the difference of proportions will be presented, together with its standard error and associated 95% exact confidence interval.

## **18. Additional Safety Analysis**

Additional to the analysis for adverse events, further safety data will be analyzed as described in this section. This analysis will be based on the Safety Population and will be presented by treatment arms as well as overall. No missing data will be imputed.

### **18.1 Analysis of Prior and Concomitant Medications**

Prior medications are defined as medications taken within 1 week of the Screening Visit until the start of IMP infusion. Concomitant medications are defined as medications with a start date and time after the start of the Day 1 infusion.

Frequency summaries of prior and concomitant medications coded with WHO drug dictionary (version Mar2020) will be provided by treatment group. Medications may also be further categorized by grouped coded terms for summary.

At each level of subject summarization, a subject is counted once if the subject reported one or more medications. A listing, including reason for use, duration, frequency and dosage of concomitant and prior medication will be provided.

### **18.2 Analysis of Prior and Concomitant Procedures**

Prior procedures are defined as procedures with a start date and time before the start of the Day 1 infusion. Concomitant procedures are defined as procedures with a start date and time after the start of Day 1 infusion.

Frequency summaries of prior and concomitant procedures and surgeries coded using MedDRA (version 23.0) will be provided by treatment group. At each level of subject summarization, a subject is counted once if the subject reported one or more procedures. A listing, including necessity of surgery and duration of concomitant and prior procedures will be provided.

### **18.3 Analysis of Additional Safety Data**

Descriptive statistics of changes from baseline to each scheduled post-baseline assessment will be provided for vital signs, laboratory test results, and radiological findings. The frequency of drug related reactions will be tabulated by visit. Listings will be provided as well.

For laboratory assessments, the shifts relative to CTCAE criteria for laboratory abnormalities will be provided. The laboratory measures will also be compared with their corresponding normal ranges, and the incidence of abnormally high and abnormally low laboratory values will be summarized.

**19. Subgroup Analysis**

Primary and secondary endpoints which demonstrate statistical significance will also be analyzed by subgroups including sex (male/female), race, ethnicity, and disease severity (according to the definitions of the electronic Case Report Forms [eCRFs]). A subgroup analysis by grouped coded terms of concomitant medications may also be provided.

**20. Change from Analysis Specified in the Corresponding Protocol Version**

Not applicable.

Property of Octapharma. Do not copy or distribute without written permission.

